8.3.5 Responder Analyses

Additional efficacy analyses may include responder analysis based on the efficacy outcomes. Since mean changes from baseline may be affected by outliers, responder analyses provide insights into drug effects that are less affected by outlier values. The following responder or categorical analyses may be conducted to complement the CBL analyses of the main efficacy outcomes including the ADAS-Cog 13, A-IADL, and CDR-SB. They may also be conducted on the MMSE and CDR-G which are part of the study inclusion criteria. Subjects with missing scores at the visits will be excluded from the responder analyses for that variable/visit. The responder categories are defined as follows:

Primary cognitive outcome, ADAS-Cog 13 (Mohs 1997):

- Number and percentage of subjects whose scores remain stable or improve from baseline (lower scores = less deficits): CBL ≤ 0 at Week 78
- Number and percentage of subjects whose scores worsen from baseline by less than:
 - o ADAS-Cog 13 CBL \leq 3.5 points at Week 78

o ADAS-Cog 13 CBL ≤ 1.5 points at Week 78

Key secondary outcome, A-IADL-IRT scores for functional categories (Dubbelman 2022a):

- Number and percentage of subjects whose A-IADL-IRT scores at Week 78 remain within the same category as baseline or improve to next higher category (higher scores = less impairment), based on the following 3 functional categories:
 - Category of "No-Mild" deficits with IRT scores \geq 50
 - Category of "Moderate" deficits with IRT scores = 40-49 inclusive
 - o Category of "Severe" deficits with IRT scores < 40

Key secondary outcomes, CDR-SB for functional categories (O'Bryant 2008):

- Number and percentage of subjects whose CDR-SB values at Week 78 remain within the same category as baseline or improve to less advanced category (lower scores = lower disease severity), based on the following 3 categories or disease stages:
 - o MCI or no impairment defined as CDR-SB from 0-4.0 inclusive
 - Mild AD defined as CDR-SB from 4.5 9.0 inclusive
 - Moderate AD defined as CDR-SB from 9.5 15.5 inclusive

Stage of AD based on CDR-G for disease stages (Morris 1993):

- Number and percentage of subjects whose CDR-G values at Week 78 remain within the same category as baseline or improve (lower scores = less severe category), based on the following 3 categories:
 - o MCI or no mpairment defined as CDR-G ≤ 0.5
 - Mild AD defined as CDR-G > 0.5 and ≤ 1.0
 - Moderate AD defined as CDR-G > 1 and \leq 2.0

Stage of AD based on baseline MMSE (Average of Screening and V2 Scores):

- Number and percentage of subjects whose MMSE values at Week 78 remain within the same category as baseline or improve to the next higher category (higher scores = milder disease), based on the following 4 categories (2 distinct sets of 4 categories):
 - o MMSE 28-30, inclusive
 - o MMSE 24-27, inclusive
 - o MMSE 22-23, inclusive

- MMSE < 22and
- o MMSE 27-30, inclusive
- o MMSE 24-26, inclusive
- o MMSE 22-23, inclusive
- o MMSE < 22

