# 5.1. Inclusion Criteria

To be considered eligible to participate in the study, the subject must meet all of the following requirements:

1. Be male or female between the ages of 50 and 80 years (inclusive) at the Screening – Part 1 Visit.

Confidential Page 41 of 115

- 2. Has a clinical diagnosis of MCI or Mild Dementia due to AD consistent with the NIA-AA Working Group Criteria [Albert et al. 2011; Jack et al. 2018; McKhann et al. 2011].
- 3. Is homozygous for the  $\varepsilon 4$  allele of the APOE gene (APOE4/4).
- 4. Has an MMSE score of 22 to 30 (inclusive) at the Screening Part 1 Visit.
- 5. Has a CDR Global score at Screening of 0.5 or 1, and a CDR Memory Box score  $\geq$  0.5.
- 6. Has an RBANS delayed memory index score  $\leq 85$ .
- 7. Has evidence of progressive memory loss over the last 12 months per investigator assessment as captured on the diagnostic verification form.
- 8. Can complete the cognitive testing and all other required study procedures.
- 9. Has completed at least 6 years of formal education after age of 5 years, and is able to read at minimum of 6th grade level or equivalent per investigator assessment.
- 10. Lives at home independently, in a senior living facility, or in an assisted living facility.
- 11. Has a body mass index (BMI) between 17-40 (inclusive).
- 12. Except for a diagnosis of AD and the presence of stable medical conditions, is, in the opinion of the Investigator, in good general medical health based upon the results of medical history, physical examination, laboratory tests, vital signs, and ECG.
- 13. Has a reliable caregiver or study partner who is willing and able to sign an ICF, to accompany the subject to study visits, and adhere to study requirements (The caregiver or study partner, in the Investigator's opinion, has adequate contact with the subject to be able to provide accurate information about the participant's cognitive and functional abilities).

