8.1.3 Definition of Study Baseline

Unless otherwise specified, baseline is defined as the last non-missing measurement obtained prior to the first dose of the study drug for all efficacy and safety measures. Values at screening visits that are the baseline for efficacy assessments will be summarized, and all other screening values will be presented in listings. The MMSE baseline is defined as the average of the scores at the screening visit and V2 visit. If the MMSE score is available from only 1 pre-dose visit (either screening or V2), that score will be used as the baseline value.

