A-IADL-IRT has a score range of 20-80 and will be calculated and transferred from a third party vendor for categorical responder analysis (Dubbelman 2022a). A-IADL-W has a score range of 0-100 and is calculated as follows: (sum of all scores / number of questions scored) × 25 which will be used for secondary efficacy analysis (Table 10, Teng 2023). For A-IADL-IRT, higher scores indicates better functioning, while for A-IADL-W, higher scores indicates worse functioning or more impairment.

If <25% (11 or fewer of 47; or 17 or fewer of 70 questions are answered) are answered as "don't know", A-IADL-W will be derived without imputation and considered valid. If the scores from more than 11 items are not available, A-IADL-W at that visit will be considered missing.

Table 10 A-IADL Algorithm for derivation of Total Score

Algorithm

If Yes is selected in main question with performance level:

No = 0

Yes, slightly more difficult = 1

Yes, more difficult =2

Yes, much more difficult =3

Yes, he/she is no longer able to perform this task =4

If No is selected in main question with performance level:

He/she was no longer able to do so due to cognitive problems = 4

He/she was no longer able to do so due to physical problems = Not scored

He/she has never done that before = Not scored

Other, please state = Not scored

A-IADL-W = (sum of all scores / number of questions scored) \times 25

CDR-SB: The CDR consists of 6 boxes for a score range of 0-18 (Table 11). It is a global rating scale used to assess the stage and severity of dementia (Morris 1993). It uses a structured, clinician-rated interview that collects information on cognitive and functional capacity from both the subject and caregiver. Higher score on CDR-SB indicates more advanced AD.

The CDR-SB will be determined by adding the individual scores from each of the six domains. The same imputation technique will be applied to missing CDR-SB boxes or sub-items. If only 1 of 6 boxes (<25%) of the CDR is missing, the sum of the boxes will be imputed by prorating the sum from the other 5 boxes: CDR-SB Total Score = Total score from the completed items × [maximum total score (=18) / maximum total score corresponding to the 5 completed boxes (=15)]. The imputed number will be derived and rounded up to the nearest integer. If more than 1 box is missing, the total score of CDR-SB at that visit will be considered missing.

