8.3.6.1 Time to Disease Progression

Additional efficacy analyses may include time-to-event (time to first disease progression) analyses using the CDR-SB and A-IADL-IRT scores. The CDR-SB analysis will evaluate the delay in progression from MCI to Mild AD stage or worse, and from Mild AD to Moderate or Severe AD (O'Bryant 2008). The A-IADL-IRT analysis will evaluate delay in functional decline, or progression from a category of "No-Mild" to "Moderate" or worse, or from "Moderate" to "Severe" functional deficits (Dubbelman 2022a). The time-to-event analyses will also be performed based on the CDR-G and MMSE scores. The categories for time-to-progression events are defined below for CDR-SB, CDR-G, A-IADL-IRT, and MMSE scores:

- CDR-SB: CDR-SB progresses from category of MCI (SB \leq 4.0) to Mild AD or worse (SB \geq 4.5); or from Mild AD (SB = 4.5-9.0 inclusive) to Moderate AD or worse (SB \geq 9.5)
- CDR-G: CDR-G progresses from MCI (CDR-G = 0.5) to Mild AD or worse (CDR-G \geq 1.0); or from Mild AD (CDR-G = 1.0) to Moderate AD or worse (CDR-G \geq 2.0)
- A-IADL-IRT: The A-IADL-IRT scores change from category of No or Mild deficits (≥ 50) to Moderate deficits or worse (<50); or from Moderate deficits (40-49 inclusive) to Severe deficits (< 40)
- MMSE: MMSE progresses from MCI (MMSE >26) to Mild AD or worse (MMSE ≤ 26); or from Mild AD (MMSE 22-26, inclusive) to Moderate AD (MMSE ≤ 21)

Time-to-Event Analysis

The time-to-event is measured from day of randomization to day of the earliest progression event (to next category). Subjects who do not experience the event by the study's end or drop out for other reasons will be censored. A Cox proportional hazard regression analysis (Cox 1972) will incorporate the treatment group and four stratification factors (use of AChEI, age group, disease severity, and gender) as covariates to determine whether there is a difference in the time to event between the ALZ-801 and placebo arms. The resulting hazard ratios, 95%

confidence intervals, and p-values will be reported. In addition, we will estimate the distribution of delaying progression in each treatment group using the Kaplan-Meier method (Kaplan 1958). The Kaplan-Meier method will provide probability estimates for patients with progression. Kaplan-Meier curves will be presented for each treatment arm, along with medians for time to progression and 95% confidence intervals.

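### In the optional category-based analyses, a subject who starts in the open-ended lowest MMSE or A-IADL-IRT category counts as a responder however far the score falls, and has no defined progression event

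*SAP*

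**What the plan says.** **Responder rule.** For MMSE stage, SAP 8.3.5 counts the "Number and percentage of subjects whose MMSE values at Week 78 remain within the same category as baseline or improve to the next higher category". Two sets of four categories are given, and both end in an unbounded category below 22. For A-IADL-IRT the rule is to "remain within the same category as baseline or improve to next higher category", and the lowest category is "deficits with IRT scores < 40". SAP 8.2.4 states that "A-IADL-IRT has a score range of 20-80", with higher scores better, so that category runs from 20 to just under 40. The only stated exclusion from the responder analyses is a missing score at the visit.

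**Baseline.** SAP 8.1.3: "The MMSE baseline is defined as the average of the scores at the screening visit and V2 visit".

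**Entry.** Protocol 5.1: "Has an MMSE score of 22 to 30 (inclusive) at the Screening Part 1 Visit". Protocol 7.1.11.6 uses that score for eligibility and the Baseline Visit score for stratification. The strata in Protocol 5.4.2 are cut at 26 and have no floor. No inclusion criterion uses A-IADL.

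**Time to progression.** SAP 8.3.6.1 defines MMSE events from above 26 to 26 or lower, "or from Mild AD (MMSE 22-26, inclusive) to Moderate AD (MMSE ≤ 21"). The A-IADL-IRT events start from 50 or more, or from 40–49. Subjects without an event are censored, and no rule removes subjects for whom no event is defined.

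**Status.** SAP 8.3.5 and 8.3.6.1 present these as additional analyses that may be done. SAP 8.1.5 treats p-values outside the graphical procedure as nominal.

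**The concern.** A rule of staying in the same category works as a success criterion only if a worse category exists. At the bottom of these two scales there is none, so for those subjects the outcome does not respond to decline. The subjects concerned are the most impaired on that scale at entry.

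Two consequences follow. Responder proportions and Kaplan-Meier progression-free estimates are raised in both arms by subjects whose success is built in, which pulls the treatment contrast toward no difference. If chance places more of these subjects in one arm, the imbalance adds a difference unrelated to treatment. SAP 8.3.5 offers the responder analyses as a complement to the change-from-baseline results, and SAP 8.3.6.1 promises hazard ratios and p-values, so readers would rely on them if they are run.

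**Working it through.** The plan gives no power, event count or expected rate for these analyses, so there is no stated figure to reproduce. The check applies the rules as written.

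**1. Can an eligible subject have an averaged MMSE below 22?** The screening score s is 22 to 30 and the V2 score v is 0 to 30. The mean is below 22 when s + v ≤ 43, that is, v ≤ 43 − s. This allows 22 values of v at s = 22, 21 at s = 23, and so on down to 14 at s = 30. The total is 9 × (22 + 14)/2 = 162 score pairs, with a highest mean of 21.5. Example: (22 + 20)/2 = 21. SAP 8.1.4 treats earlier screening scores below 22 as screen failures; that concerns repeat screening and sets no limit at V2.

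**2. How are these subjects classified?**

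| Baseline → later score | Responder (8.3.5) | Event (8.3.6.1) |
|---|---|---|
| MMSE 21 → 5 | yes | none defined |
| MMSE 22 → 21 | no | yes |
| A-IADL-IRT 39 → 20 | yes | none defined |

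For all 162 pairs and both category sets, every lower Week 78 MMSE is a responder and no later score is an event. No A-IADL-IRT event starts from below 40. The CDR-SB and CDR-G responder categories are capped at 15.5 and 2.0, so this open-ended problem is confined to MMSE and A-IADL-IRT.

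**3. Effect on the contrast.** If a share f always responds in both arms, the observed rate is f + (1 − f)p and the difference is (1 − f)(p₁ − p₀). Illustration with true rates of 60% and 45% (assumed), a difference of 15 points:
- f = 1%: 15 × 0.99 = 14.85 points
- f = 5%: 15 × 0.95 = 14.25 points
- f = 9%: 15 × 0.91 = 13.65 points

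Each arm's rate rises by f(1 − p). At f = 5% that is 0.05 × 0.40 = 2.0 points and 0.05 × 0.55 = 2.75 points.

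**4. Size of f for MMSE.** The documents give only the expected 60/40 split between MMSE 22–26 and 27–30, and 325 randomised (SAP 4.1). Everything else here is assumed.
- *V2 scattered around the observed screening score.* Screening is uniform within 22–26 (0.12 per score) and within 27–30 (0.10 per score); V2 minus screening is normal with mean 0 and SD σ. Then f = Σ p(s) Φ((43.5 − 2s)/σ). σ = 1 gives 3.8% (12.3 of 325), σ = 2 gives 6.2% (20.3), and σ = 3 gives 8.7% (28.1).
- *Both scores scattered around a true score.* This allows for regression to the mean. True scores are normal with SD 2 or 3, with the mean set to reproduce the 60/40 split among eligible subjects; visit error SD is 1 to 2; scores are rounded and capped at 30. This gives 0.8% to 4.7% (2.5 to 15.2 of 325).

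Together the range is roughly 1% to 9%, about 2 to 28 subjects. The share with baseline A-IADL-IRT below 40 cannot be derived from the documents.

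**The case against.** **Low stakes.** These analyses are optional and nominal, and no confirmatory conclusion rests on them. A fall from MMSE 21 to 5 counts in full in the MMRM of MMSE change (SAP 5.2.2 and 8.3.3). This stands, and it caps the importance of the point.

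**The effect is small and does not favour the drug.** Equal shares in both arms pull the difference toward zero, and under randomisation unequal shares arise by chance. This stands. A reader might infer a built-in bias for active treatment; the rules are the same in both arms and do not support that.

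**The numbers are soft.** A reader might want a single count of affected subjects. The documents give no visit-to-visit MMSE variability, and the two models above differ roughly tenfold at their extremes, so only the range is defensible. Nor is every subject with a low baseline an automatic responder: those without a Week 78 score are excluded, and about 17% dropout is expected. Entry at CDR-Global 0.5 or 1 may also keep the A-IADL-IRT share low.

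**SAP 8.3.6.1 can be read more kindly.** Its event list could be taken to limit the analysis to subjects in the starting stages. The event definitions also do not say that progression is judged from baseline, so a subject who rises to 22–26 and later falls to 21 or below might count. An unconditional claim that these subjects can never have an event is therefore too strong. But no exclusion is written, and on the natural reading, from baseline category, the gap remains.

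**Conclusion.** The point holds as a minor defect in optional, nominal analyses. It is a stated rule that gives a wrong answer for an identifiable group: subjects with an averaged MMSE below 22, or A-IADL-IRT below 40, at baseline. With a Week 78 score they are responders after any decline; judged from baseline category they have no progression event on that scale but are censored as progression-free.

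The main consequence is attenuation by the factor (1 − f). At the assumed MMSE range of roughly 1% to 9%, a 15-point difference would become about 14.9 to 13.7 points. The A-IADL-IRT effect cannot be sized.

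A reader might infer that the key secondary A-IADL result is affected. It is not: that endpoint is change in A-IADL-W, whereas the categories use A-IADL-IRT. The ADAS-Cog 13 and CDR-SB change analyses are likewise untouched.

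**What to change.** - **SAP 8.3.5 (MMSE and A-IADL-IRT):** restrict the responder denominator to subjects whose baseline category allows worsening by at least one category, that is, averaged MMSE of 22 or more, or A-IADL-IRT of 40 or more.
- **SAP 8.3.6.1:** exclude from each scale's risk set subjects whose baseline is already in that scale's worst category, and state that progression is judged from the baseline category. For MMSE write the limit as below 22 rather than 21 or lower, so that an averaged baseline of 21.5 is covered.
- **Both sections:** report the number excluded by arm.

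An alternative is to keep these subjects and call them responders only if the score does not fall at all. That would hold them to a stricter rule than everyone else: 21.5 to 21 would fail, while 27 to 24 stays a success in the first MMSE set. Restricting the denominator keeps one rule for all.

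The cost is a few sentences and no new data. The downside is a few subjects fewer in each analysis and slightly lower responder rates. The change should be made before unblinding, so that the choice cannot depend on the results.

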8.3.6 Time to Event Analyses

[figure not shown]
8.3.6.1 Time to Disease Progression

Additional efficacy analyses may include time-to-event (time to first disease progression) analyses using the CDR-SB and A-IADL-IRT scores. The CDR-SB analysis will evaluate the delay in progression from MCI to Mild AD stage or worse, and from Mild AD to Moderate or Severe AD (O'Bryant 2008). The A-IADL-IRT analysis will evaluate delay in functional decline, or progression from a category of "No-Mild" to "Moderate" or worse, or from "Moderate" to "Severe" functional deficits (Dubbelman 2022a). The time-to-event analyses will also be performed based on the CDR-G and MMSE scores. The categories for time-to-progression events are defined below for CDR-SB, CDR-G, A-IADL-IRT, and MMSE scores:

- CDR-SB: CDR-SB progresses from category of MCI (SB \leq 4.0) to Mild AD or worse (SB \geq 4.5); or from Mild AD (SB = 4.5-9.0 inclusive) to Moderate AD or worse (SB \geq 9.5)
- CDR-G: CDR-G progresses from MCI (CDR-G = 0.5) to Mild AD or worse (CDR-G \geq 1.0); or from Mild AD (CDR-G = 1.0) to Moderate AD or worse (CDR-G \geq 2.0)
- A-IADL-IRT: The A-IADL-IRT scores change from category of No or Mild deficits (≥ 50) to Moderate deficits or worse (<50); or from Moderate deficits (40-49 inclusive) to Severe deficits (< 40)
- MMSE: MMSE progresses from MCI (MMSE >26) to Mild AD or worse (MMSE ≤ 26); or from Mild AD (MMSE 22-26, inclusive) to Moderate AD (MMSE ≤ 21)

Time-to-Event Analysis

The time-to-event is measured from day of randomization to day of the earliest progression event (to next category). Subjects who do not experience the event by the study's end or drop out for other reasons will be censored. A Cox proportional hazard regression analysis (Cox 1972) will incorporate the treatment group and four stratification factors (use of AChEI, age group, disease severity, and gender) as covariates to determine whether there is a difference in the time to event between the ALZ-801 and placebo arms. The resulting hazard ratios, 95%

confidence intervals, and p-values will be reported. In addition, we will estimate the distribution of delaying progression in each treatment group using the Kaplan-Meier method (Kaplan 1958). The Kaplan-Meier method will provide probability estimates for patients with progression. Kaplan-Meier curves will be presented for each treatment arm, along with medians for time to progression and 95% confidence intervals.

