# 5.5. Subject Withdrawal, Termination, and Replacement

Study subjects may discontinue from the study or be withdrawn from the study for any of the following reasons:

- At the subject's or the subject's legally authorized representative with the subject's assent request for any reason (withdrawal of consent)
- Subject whose cognitive function declines and is deemed by the Investigator to be unable to provide assent/consent for continuation in the study
- At the discretion of the Investigator, if deemed appropriate, for any reason
- At the discretion of the Sponsor, if deemed appropriate, for any reason
- Subject for whom investigator deems initiation of memantine medically necessary must be withdrawn
- Subject noncompliance: If a subject takes less than 70% of study drug tablets, this may be considered reason for withdrawal, by Investigator or Sponsor request
- Protocol violation that compromises subject safety
- For safety concerns; medically significant AE(s) or SAE(s) with CTCAE > Grade 3 may be considered reason for withdrawal, if appropriate in the judgment of the Investigator
- Subject who becomes pregnant must be withdrawn from the study
- The subject's caregiver/study partner is no longer willing or able to participate in the study and a suitable replacement caregiver/study partner cannot be found
- Brain MRI findings: subject who has any of the following findings on central reading:
  - o Macrohemorrhage: defined as hemorrhage with size > 1 cm^3
  - o ARIA-E (vasogenic edema) associated with neurologic symptoms: dosing will be halted for 1 month and MRI repeated. Resumption of dosing may be considered after discussion between Investigator and Sponsor's medical officer.
- Subject who experiences an event of syncope without a clear triggering event (e.g., blood draw or pain inducing a vasovagal episode) will be withdrawn from the study
- Subject with clinically notable ECG abnormalities based on the average of triplicate ECG readings. The criteria for clinically notable or significant ECG results that require subject withdrawal are as follows:
  - o QTcF (Fridericia's correction) interval > 500 msec, and
  - An increase in QTcF interval of > 60 msec from baseline.

Confidential Page 51 of 115

**Note:** The criteria for QTcF are based on the upper threshold in elderly subjects who are known to have higher ULN [Reardon & Malik, 1996], and is the threshold commonly used in AD studies.

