8.1.5 Multiplicity of Secondary Endpoints

The graphical approach will be used on testing multiple endpoints in a predefined order to strongly control the family-wise type 1 errors arising from multiple comparisons (Bretz 2009). The alpha recycle is described in detail in Figure 2. For the primary efficacy endpoint (CFBL to week 78 in ADAS-Cog 13, i.e., H1) hypothesis testing, the initial 2-sided significance level is set to 0.05. Only if the H1 testing is successful will the next two key secondary endpoints: CFBL to week 78 in A-IADL (H2) and CFBL to week 78 in CDR-SB (H3), be tested each at an alpha level of 0.025. If H2 shows significance, its alpha level of 0.025 is passed on to H3 for testing at an endpoint-specific alpha level of 0.025+0.025=0.05. However, if H2 is not significant, H3 is still tested at the reserved alpha level of 0.025. In this scenario, if H3 turns out to be significant, the alpha level for H2 is recycled back for re-testing at 0.05.

Since a graphical approach is used in the analysis, the overall type I error rate is strongly controlled at the 2-sided α =0.05. The hypothesis testing for the additional clinical endpoints (not presented in Figure 2) will be done without control for type I errors due to multiple comparisons and the p-values will be considered nominal.

8.2 Visit Windows and Efficacy Data Algorithms and Definitions/Handling of Dropouts or Missing Data

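### The time-to-progression analyses censor, as if uninformative, subjects withdrawn for cognitive decline or needed memantine before crossing a stage threshold; one supplementary analysis would show how much this matters

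*SAP*

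**What the plan says.** SAP 8.3.6.1 defines progression only by movement between score categories on CDR-SB, CDR-G, A-IADL-IRT or MMSE. Under its censoring rule, subjects who have no event by the study's "end or drop out for other reasons will be censored". The SAP does not say which reasons are meant. On the model: "A Cox proportional hazard regression analysis (Cox 1972) will incorporate the treatment group and four stratification factors". Kaplan-Meier curves, probabilities and medians are reported as well. The section gives no sensitivity analysis for censoring.

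The analysis is optional: "Additional efficacy analyses may include time-to-event (time to first disease progression) analyses using the CDR-SB and A-IADL-IRT scores". It lies outside the testing procedure of SAP 8.1.5, where for such endpoints "the p-values will be considered nominal".

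Two of the withdrawal reasons in Protocol 5.5 describe worsening disease: "Subject whose cognitive function declines and is deemed by the Investigator to be unable to provide assent/consent for continuation in the study" and "Subject for whom investigator deems initiation of memantine medically necessary must be withdrawn".

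Three other places bear on what is observed after withdrawal:
- Protocol 7.2.14 schedules CDR, A-IADL and MMSE at the early-termination visit, and SAP 8.2.1 maps that visit to an analysis window.
- Protocol 7.2.15 encourages, but does not require, retrieved-dropout visits at Weeks 52 and 78. These collect A-IADL and MMSE but not CDR.
- SAP 8.1 undertakes to separate intercurrent events from uninformative withdrawals in the efficacy analyses, but 8.3.6.1 does not carry this through.

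**The concern.** Cox and Kaplan-Meier assume that a censored subject has the same future risk as subjects still followed in the same arm (for Cox, with the same covariates). Someone removed because cognition has failed, or because the investigator judges memantine necessary, is probably nearer the next stage than those who remain. If that person has not crossed a threshold by the early-termination visit, the event will usually never be seen on CDR, and the estimator fills in an average future. Progression is then understated in whichever arm loses such subjects.

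What is at stake is a set of hazard ratios, progression probabilities and median times that could be quoted as evidence of delayed progression, with nothing beside them to show how far they depend on this assumption.

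**Working it through.** **What the plan gives.** There is no progression rate, event count, hazard ratio or power for this analysis to reproduce. The usable figures are in SAP 4.1: 300 x 0.83 = 249, which matches the stated 250 or so completers. With 325 randomised 1:1 there are about 162 per arm, and 17% of 325 is about 55 dropouts, with no split by reason.

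**Assumptions (none from the documents).** Cumulative progression F at Weeks 26, 52 and 78 among subjects not withdrawn for these reasons is 14/27/40%, or 10/20/30% as an alternative. A fraction w of an arm is withdrawn for one of the two reasons before crossing, w/3 in each CDR interval.

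**Step 1, hazards.** h_k = (F_k - F_(k-1)) / (1 - F_(k-1)) = 0.1400, 0.1512, 0.1781 (alternative: 0.1000, 0.1111, 0.1250).

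**Step 2, planned analysis.** Withdrawals only leave the risk set, so S = product of (1 - h_k) = 0.60 and estimated progression is 40% (alternative 30%), whatever w is.

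**Step 3, withdrawals counted as progression.** S_k = (S_(k-1) - w/3)(1 - h_k). For w = 5% in the 40% case:
- (1 - 0.0167) x 0.86 = 0.8457
- (0.8457 - 0.0167) x 0.8488 = 0.7037
- (0.7037 - 0.0167) x 0.8219 = 0.5647

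Progression is 43.5%, so the planned estimate is 3.5 points lower.

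| w | subjects of 162 | gap, 40% case | gap, 30% case |
|---|---|---|---|
| 2% | 3.2 | 1.4 | 1.6 |
| 4% | 6.5 | 2.8 | 3.1 |
| 5% | 8.1 | 3.5 | 3.9 |
| 8% | 13.0 | 5.7 | 6.3 |

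The single-arm standard error is sqrt(0.40 x 0.60/162) = 3.85 points (alternative: sqrt(0.30 x 0.70/162) = 3.60). In the 40% case the gap reaches half a standard error at w of about 2.7%.

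**Step 4, hazard ratio.** Take HR 0.70 among subjects not withdrawn for these reasons, so drug hazards are 1 - (1 - h_k)^0.70. Planned drug progression is 1 - 0.60^0.70 = 30.1%, a difference of 9.9 points. Counting withdrawals, HR = ln S(drug) / ln S(placebo) at Week 78. Placebo has w = 6%, which gives 44.2%.

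| w placebo v drug | drug progression | HR, 40% case | difference, 40% case | HR, 30% case |
|---|---|---|---|---|
| 6% v 3% | 32.4% | 0.67 | 11.8 | 0.66 |
| 6% v 4.2% (= 0.70 x 6%) | 33.4% | 0.69 | 10.9 | 0.69 |
| 6% v 6% | 34.8% | 0.73 | 9.5 | 0.74 |

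For the first row, ln 0.676 / ln 0.558 = 0.67.

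**Step 5, a second model.** Let a share q of would-be progressors leave just before the visit, so the Kaplan-Meier hazard becomes h(1 - q)/(1 - qh). With 45% placebo progression, equal interval hazards and true HR 0.70, placebo h = 1 - 0.55^(1/3) = 0.181.
- q = 20% in both arms: 38.6% v 28.8% instead of 45.0% v 34.2%; HR stays at 0.70.
- q = 20% placebo, 10% drug: 38.6% v 31.6%; HR 0.78. If 50% or 90% of these crossings are caught at the early-termination visit, HR is 0.73 or 0.71.
- q = 10% placebo, 20% drug: HR about 0.63, which favours the drug.

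Both models agree: progression is understated, and the hazard ratio moves according to relative imbalance.

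**The case against.** **A reader might infer that the rule pulls the hazard ratio toward 1 whenever placebo has more of these withdrawals, so that a real benefit is diluted.** The documents do not support that. At 6% v 4.2% placebo has more, yet the ratio barely moves. The 0.67 arises only because 6% v 3% assumes a stronger drug effect on withdrawal (ratio 0.5) than on progression (0.70). Nothing in either document predicts the balance.

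**A reader might also infer that everyone withdrawn for these reasons is censored.** That is too broad. A crossing recorded at the early-termination visit counts, and subjects who have lost capacity or need memantine may well have crossed by then. For A-IADL-IRT and MMSE, retrieved-dropout scores can add later events: SAP 8.3.1 says all collected data are used, and SAP 8.3.3 applies treatment policy to the secondary endpoints. An explicit line on those scores in 8.3.6.1 would be a clarification only.

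**The single-arm yardstick flatters the concern.** On the contrast between arms, the 6% v 3% case moves the difference by 11.8 - 9.9 = 1.9 points, against a standard error of sqrt(0.40 x 0.60/162 + 0.301 x 0.699/162) = 5.3 points, or 0.36 of a standard error. This is fair, and it keeps the point small.

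**Counting withdrawal as progression changes the estimand.** This also stands. The 0.67 and 0.73 belong to a composite event and are not corrected values of the planned hazard ratio. That is why the added analysis should sit beside the planned one.

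What survives is that subjects withdrawn for decline before crossing are treated as uninformative, CDR is not collected from them afterwards, and 8.3.6.1 has no check on the assumption.

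**Conclusion.** The point holds in a limited form. Censoring under SAP 8.3.6.1 is informative for subjects withdrawn for either reason who have not crossed by the early-termination visit, mainly on CDR-SB and CDR-G. Kaplan-Meier progression in the affected arm is understated by about 1.4-1.6 points at 2% affected and 3.5-3.9 points at 5%. These sizes assume 30-40% progression and that every affected subject would have progressed by Week 78; if only some would have, the understatement is smaller. For scale, 5% would be nearly a third of the planned 17% dropout (5/17 = 29%), and the true fraction is unknown.

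No direction can be claimed for the hazard ratio. The planned figure is nearer 1 than the composite only if these withdrawals are more unbalanced against placebo than progression itself. It is about unchanged if they mirror progression, and it flatters the drug if they are equal in number. Because the analysis is optional and its p-values nominal, the primary and key secondary conclusions are untouched. This is a low-severity improvement, best settled before unblinding because the direction cannot be known in advance.

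**What to change.** Add to SAP 8.3.6.1 one pre-specified supplementary Cox and Kaplan-Meier analysis. In it, withdrawal for cognitive decline with loss of capacity to assent or consent, or for medically necessary memantine, counts as a progression event on the withdrawal date, unless a category change was recorded earlier. Keep the planned analysis as it is and report the two together. Optionally, add one sentence confirming that category changes at early-termination and retrieved-dropout visits count as events.

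The cost is a short paragraph and one extra run. Protocol 5.5 already requires the discontinuation reason on the eCRF, and Protocol 7.1.8 records medications. The documents do not show whether the coded reasons separate these two categories, so a blinded check should confirm that both can be identified. The downside is that the supplementary event includes an investigator's decision, which is a reason to add it and not to substitute it. No withdrawal rule changes.
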